6.2 Clinical Management of Adverse Events

Events will be managed by the clinical trial team who will assess and treat the event as appropriate, including referral to an independent physician and/or the participant's General Practitioner if required.

See also **section 7.4**

6.3 Non-Trial Treatment

As stated in the exclusion criteria in **Section 4.2**, participants should not have received other immunisations, immunosuppressive agents, blood products, immunoglobulin or other trial medication within specified periods prior to enrolment. This applies during the trial through to the final safety visit 22 weeks after enrolment, 2 weeks after the last scheduled immunisation, unless the treatment is required for an emergency.

Should a participant require immunisation for the purposes of travel, occupation or other clinical need during the trial, the request will be reviewed by the Trial Management Group who will advise on timing and whether or not the trial immunisation schedule needs to be amended.

Participants will be allowed to continue with hormonal contraception if this forms part of their regular appropriate contraception plan. The precise method will be recorded on the screening CRF and any changes on the concomitant medication CRF.

All concomitant medication will be recorded on the CRF, including any dispensed by the investigators in the management of adverse events or reactions.

6.4 Issues Related to HIV

Only volunteers with a negative 4th generation HIV antibody/antigen result will be enrolled onto the study.

A 4th generation HIV antibody/antigen assay, the standard laboratory method for diagnosing HIV infection, will be used to screen volunteers after they have received appropriate counselling. An HIV test will be performed at two time-points in the study: the screening visit, and the visit 4 weeks after the final vaccination, unless clinically indicated at other times.

At each immunisation visit a risk assessment will be conducted and an additional HIV test will be performed if there has been a change in risk status. Participants will be counselled by study personnel about the importance of condoms and reminded on the day of each immunisation. Hypo-allergenic condoms will be provided free of charge.

In the event that any blood specimen is positive, participants will be invited for confirmatory tests to distinguish between vaccine-induced seropositivity and genuine HIV infection. Participants with vaccine-induced seropositivity will be provided with appropriate certification of their HIV status, and retested at the visit 6 months after the final vaccination. If that test is positive also, they will be invited to return to the clinical centre for re-testing until such time as the test becomes negative.

6.4.1 Verification of HIV status of participants

In the event of an equivocal or positive result, a specimen will be processed through a range of assays according to the local laboratory operating procedures to establish the HIV status of the individuals. A confirmatory specimen will be collected at a later date, if the first result suggests that the participant is HIV infected.

If a participant requires certification independent of the local laboratory, then this can be arranged through the clinic team.

6.4.2 HIV infection

In the unexpected circumstances that a participant in the trial acquires HIV infection, they will be referred for clinical care and counselling.

7. ASSESSMENTS AND FOLLOW-UP

7.1 Duration of Follow-up and Schedule

The assessments that will be performed at each visit are described in **Table 5**.

Participants will be required to make a minimum of 11 scheduled outpatient visits over the course of up to 30 weeks. Time 0 will start on the day of enrolment, which is also the day of randomisation and first immunisation.

Screening can take place up to 6 weeks (42 days) before time 0.

Immunisations will take place at weeks 0, 4, 8 and 20.

A 12th scheduled outpatient visit, at Week 44, will only take place for participants known to have responded to the vaccine.

Serum will be collected for immunogenicity at enrolment, and weeks 4, 5, 8, 9, 20, 21, 22 (the primary endpoint), 24 and 44. Peripheral blood mononuclear cells (PBMC) will be collected at enrolment, and weeks 4, 8, 20, 21, 22, 24 and 44.

Adverse events will be assessed during the enrolment visit before and after immunisation and at every visit thereafter up to (and including) Week 22. Routine laboratory safety parameters will be collected at screening, enrolment, and weeks 1, 4, 5, 8, 9, 20, 21 and 22, and at any other visit if clinically indicated.

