7.4 Procedures for Assessing Safety and Tolerability

7.4.1 Adverse Event Assessment

Information on adverse events will be collected through a structured interview at scheduled visits as indicated in **Table 5**.

The investigator will record the diagnosis or the symptoms if a diagnosis is not apparent, the date of onset and the date of resolution if appropriate. For events not specified in the tables in study specific toxicity grading table (**Appendix 2**) the severity will be determined according to the FDA guidance (2007)

<http://www.fda.gov/downloads/BiologicsBloodVaccines/GuidanceComplianceRegulatoryInformation/Guidances/Vaccines/ucm091977.pdf>

The seriousness of the event and its relationship to vaccine will be determined by the investigator according to the definitions provided in **section 8**. All of this information will be recorded in the adverse event CRF.

7.4.2

General Examination and Vital Signs

General examinations will be done at screening and on dosing days, as per **section 7.2.1** (height and weight at screening only). General examinations at other visits per **Table 5** will be done only if clinically indicated. Assessment of vital signs (blood pressure, pulse, respiratory rate and oral temperature) will be performed at all visits up to Week 22.

7.4.3

Routine Laboratory Parameters and Urinalysis

A pregnancy test will be performed by analysis of a urine sample for Human Chorionic Gonadotrophin (HCG) collected from women of child-bearing potential at screening, the day of each immunisation and at the final safety visit (Week 22). The analysis will be conducted by a member of the study team.

Peripheral blood and urine will be collected and analysed, as described in **section 7.2.3**, for the following parameters at the time points specified in **Table 5**, and at additional time points if indicated to further evaluate or follow up adverse events:

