7.4.5 Non-solicited Adverse Events

Non-solicited AEs starting from the first vaccination until the final safety visit (Week 22) will be captured and reported on the adverse event CRF. When making a non-solicited AE enquiry, staff should ask a non-leading question such as 'how have you been feeling?'

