8.2 Reporting Adverse Events

Adverse events should be recorded on the appropriate CRF.

All **SAEs** should be reported to the sponsor within 24 hours of the Clinical Investigator becoming aware of the event fulfilling the criteria. The SAE form should be completed and e-mailed to the Project Manager/Monitor and the Joint Research Compliance Office. The minimum criteria required in reporting a SAE are the participant identifiers (trial number/date of birth), reporting source (name of Investigator), and why the adverse event is identifiable as serious.

Other important adverse events that should be reported to the sponsor within 24 hours of the Clinical Investigator becoming aware of the event, include

- allergic bronchospasm requiring intensive emergency treatment
- a seizure
- any adverse event that results in **discontinuation of the immunisation schedule**
- any adverse event that requires intervention to prevent a threat to life or death

SAE AND IMPORTANT AE NOTIFICATION

Within 24 hours of becoming aware of an SAE or Important AE, please enter onto the SAE CRF and indicate as serious and email the MRC CTU at UCL [contact] and the Imperial College London Joint Research Compliance Office at [contact]

SAE AND IMPORTANT AE NOTIFICATION

Faxes and emails should be acknowledged by the MRC CTU immediately on receipt. If the Clinical Investigator does not receive an acknowledgement they will assume that MRC CTU is not aware of the event and use an alternative method of notification.

The Principal Investigator will ensure that the SAE form is sent within 24 hours of an event. The Chief Investigator will assess whether the event qualifies in seriousness and relationship as a **Suspected Unexpected Serious Adverse Reaction (SUSAR)**. Fatal and life-threatening SUSARs must be reported to the MHRA within 7 days of day 0 which is defined as the day the sponsor became aware of the event. Relevant follow-up information should be sought and a further report completed as soon as possible and submitted within 8 additional days. SUSARs which do not result in death or a threat to life should be reported within 15 days of day 0. Ultimate responsibility for classification resides with the study Sponsor.

[figure not shown]
Investigators should notify the JRCO of all SAEs occurring from the time of randomisation until 30 days after the last protocol treatment administration. SARs and SUSARs must be notified to the JRCO until trial closure.

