9. WITHDRAWAL OF PARTICIPANTS

Withdrawal from the trial means stopping all further visits.

The reason(s) for withdrawal should be recorded on the Status CRF.

All participants are free to withdraw from the trial at any time, for any reason, without affecting their future medical care. An investigator may decide to withdraw a participant if the investigator deems that continuing might compromise participant wellbeing or interfere with the achievement of the trial's objectives.

Participants who are withdrawn due to an adverse event (AE) will be followed-up until the event has stabilised.

Withdrawn participants who have received any immunisations should be asked to undergo the procedures scheduled for the primary endpoint visit (Visit 10, week 22).

Policy for replacing withdrawals

Additional volunteers will be enrolled to replace early withdrawals or those who have discontinued their immunisations early, with the aim of having 24 subjects complete the study with no major protocol deviations. However, no more than 30 individuals in total will be exposed to the vaccine.

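### Scheduled adverse event enquiry stops two weeks after the boost although SAEs are notifiable for 30 days, and the withdrawal visit omits the scheduled post-vaccination HIV test

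*Protocol*

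**What the plan says.** **Adverse event enquiry.** Protocol 7.1 ends it at week 22: "Adverse events will be assessed during the enrolment visit before and after immunisation and at every visit thereafter up to (and including) Week 22". Section 7.4.5 uses the same end date: "Non-solicited AEs starting from the first vaccination until the final safety visit (Week 22) will be captured". The last dose, the CN54gp140 boost, is at week 20: "Immunisations will take place at weeks 0, 4, 8 and 20".

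**Reporting duty.** Section 8.2 asks investigators to notify "all SAEs occurring from the time of randomisation until 30 days after the last protocol treatment administration". SARs and SUSARs stay notifiable until the trial closes.

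**Visit 11 (week 24).** Section 7.1 counts it among the minimum 11 visits. Serum and PBMC are collected, and Table 5 adds an HIV test and a urine pregnancy test. Table 5 labels it a response follow-up; visit 10 is the final safety visit.

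**Withdrawal.** Under section 9, vaccinated participants who withdraw "should be asked to undergo the procedures scheduled for the primary endpoint visit (Visit 10, week 22").

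**HIV testing.** Section 6.4 sets two routine time points: "the screening visit, and the visit 4 weeks after the final vaccination". Other tests depend on clinical indication or a change in risk status.

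**Pregnancy testing.** Section 7.4.3 places tests at screening, "the day of each immunisation and at the final safety visit (Week 22"). Table 5 puts the last one at week 24.

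**The concern.** The duty to notify SAEs outlasts the period in which anyone is scheduled to ask about them. An event in the second half of the 30 days reaches the investigator only if the participant, the GP or someone else raises it. This follows the only dose of the protein component, and participants are in the clinic close to day 30 anyway.

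The exit procedures have a similar mismatch. The protocol treats equivocal HIV results after vaccination as an ethical issue (13.1), and 6.4 provides certification and retesting once a specimen is positive. A vaccinated participant who leaves through visit 10 has no scheduled test that would start that process. What is at stake is a participant leaving without knowing that a standard HIV test may read positive.

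The two pregnancy-test dates matter for the same people. If Table 5 is followed, someone leaving through visit 10 also misses the last scheduled pregnancy test; if 7.4.3 is followed, they have it.

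**Working it through.** **Inputs.** Dose 4 at week 20 and last enquiry at week 22 (7.1); ±3 days for weeks 22 and 24, counted from dose 4 (7.1.2); SAE notification to day 30 after the last dose (8.2).

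**Plan's own figure.** Section 6.3 places the final safety visit 2 weeks after the last scheduled immunisation. (22 − 20) × 7 = 14 days, which agrees.

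**Days not covered by a scheduled question** = 30 − (day of last enquiry after dose 4), not below 0:

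| Last enquiry | Day after dose 4 | Uncovered days of 30 |
|---|---|---|
| Week 22, on target | 14 | 30 − 14 = 16 |
| Week 22, 3 days late | 17 | 30 − 17 = 13 |
| Week 22, 3 days early | 11 | 30 − 11 = 19 |
| Week 24, on target | 28 | 30 − 28 = 2 |
| Week 24, 3 days late | 31 | 0 |
| Week 24, 3 days early | 25 | 30 − 25 = 5 |

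As planned, scheduled enquiry covers 14/30 = 47% of the SAE period (11/30 = 37% to 17/30 = 57%). A question at visit 11 cuts the shortfall from 13–19 days to 0–5. It closes it fully only when the visit falls 2 or 3 days late, since day 30 is week (140 + 30)/7 = 24.3. SAP 4.3 gives week 22 a wider ±7 days; on that window the last enquiry is at day 7–21 and the present gap is 30 − 21 = 9 to 30 − 7 = 23 days. The protocol window is used here.

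**Is there an adverse event question at week 24?** The Table 5 row for adverse events and concomitant medication is broken in the text extraction available for this review: entries stop at week 4. It can neither confirm nor exclude a week-24 entry. The point therefore rests on 7.1 and 7.4.5, both of which end at week 22. The intact rows for vital signs and safety bloods also stop at week 22.

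**HIV test at exit.** The Table 5 row is mandatory at screening and week 24, conditional at weeks 0, 4, 8, 20 and 44, and blank at week 22. This agrees with 6.4, because 4 weeks after dose 4 is week 24. Visit 10 procedures therefore include no HIV test, and section 9 names only visit 10.

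**Pregnancy test.** The Table 5 row has entries at screening and weeks 0, 4, 8, 20 and 24, with none at week 22. Its last entry is in the same column as the mandatory HIV test, whose position 6.4 confirms independently. Section 7.4.3 says week 22. The two cannot both be the schedule.

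**The case against.** The strongest reply is that active collection and a notification duty are different things. Sections 7.1 and 7.4.5 say when staff ask; 8.2 says what must be passed on once known. Different end dates can coexist, so this is not a strict contradiction. That stands.

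The passive routes are also real. Participants can call the clinic, with 24-hour cover (13.2); extra visits are allowed (7.1.1); known events are followed to resolution or stabilisation (7.4.6); GPs are told of participation (12.6); and SAEs are by nature hard to overlook. These lower the chance of a miss but do not replace a question. A reader might infer that the SAE count must be incomplete; the documents show only that part of it depends on unprompted reporting.

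A reader might also infer that safety results become biased by arm, because the week-44 visit "will only take place for participants known to have responded to the vaccine". The documents do not support this. The text schedules no adverse event enquiry at week 44 for responders either, and SAP 3.1.1 counts primary safety events from week 0 to week 22, so no planned safety comparison uses later events.

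Nor does week 24 lack all safety content: Table 5 gives it HIV and pregnancy tests. Only the adverse event question is missing.

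On leavers, a clinically indicated HIV test remains possible (6.4), and 13.1 says routine assays can separate a vaccine response from infection. But a change in risk status would not flag vaccine-induced seropositivity, and certification starts only after a positive result. It is tempting to take the replacement allowance in section 9 (30 exposed less 24 completers, so 6) as the number affected. It is not: it includes participants who only stop dosing, and 6.1.5 keeps those who agree in follow-up with samples at the usual times, so they can reach visit 11.

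**Conclusion.** The concern holds in limited form. For participants who receive dose 4, 13–19 of the 30 SAE-notifiable days rely on passive reporting, although a visit attended by all continuing participants falls on days 25–31. This rests on the protocol's visit windows and on the text of 7.1 and 7.4.5, not on the broken Table 5 row. The size is given in days, because the documents supply no event rate from which to estimate missed SAEs.

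Separately, vaccinated participants who withdraw fully have no scheduled post-vaccination HIV test at exit. The documents do not say how many that would be.

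The final pregnancy-test date is inconsistent between 7.4.3 and Table 5.

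None of this alters the planned safety or immunogenicity comparisons. These are gaps in safety follow-up that are cheap to close.

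**What to change.** 1. In 7.1, 7.4.5 and Table 5, add a brief adverse event, SAE and concomitant medication question at visit 11. Align the SAE capture end date with the 30 days in 8.2, so that the 0–5 days the visit may leave are covered by the stated capture period.
2. Reconcile the exit procedures in section 9 with 6.4 and Table 5, so that the post-vaccination HIV test is offered to vaccinated participants who withdraw.
3. Reconcile the final pregnancy-test date between 7.4.3 and Table 5, and make the section 9 exit list consistent with the result.

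Cost: one protocol amendment, one CRF page, and one test already in the protocol at exit for those who withdraw. No clinic visit is added. The SAP window of week 0 to week 22 for primary safety endpoints can stay as it is.

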7.1.1 Additional Visits

Additional visits and assessments may be required to evaluate an adverse event, and/or identify a diagnosis. These are compatible with the protocol.

Referral to an independent specialist with the appropriate expertise will be arranged if there is uncertainty about the relationship of an adverse event to study vaccine.

7.1.2 Visit Windows

The second, third and fourth immunisation visits scheduled for weeks 4, 8 and 20 will be compliant with the protocol if they take place ± 3 days either side of the target date determined by the date of the previous vaccination. If there is a delay >4 weeks a decision will be made by the trial management group (TMG see **section 16.1**) as to whether immunisation will continue.

The post-immunisation safety visits scheduled for weeks 1, 5 and 9 will be compliant with the protocol if they take place -3 to +7 days of the target date determined by the date of the previous vaccination. The safety visit at Week 21 will be compliant with the protocol if it takes place -3 to +3 days of the target date.

The primary endpoint and follow-up visits scheduled for weeks 22 and 24 will be compliant with the protocol if they take place ± 3 days either side of the target date determined by the date of the fourth vaccination.

The follow-up visit scheduled for week 44 will be compliant with the protocol if it takes place ± 14 days either side of the target date determined by the date of the fourth vaccination.

7.2 Screening Assessments

7.2.1 Demographics, Medical History and Examination

Demographic information such as age, and ethnic origin will be collected at screening and entered onto the screening CRF.

A past and current medical history will be collected at screening during a face to face structured interview using a case report form, including details of any previous reaction to vaccination, allergies, history of epileptic fit, reproductive and respiratory symptoms, contraceptive practices (current method and the length of time using the method), and smoking, alcohol, steroid use and illicit drug history.

The general examination will include weight (kg), height (cm), calculation of BMI, temperature, arm and thigh circumference, blood pressure, inspection of the skin to exclude severe eczema and respiratory, cardio-vascular, abdominal, and neurological examination. Skin fold thickness will be assessed within the upper right and left thigh. An assessment of cervical, axillary and inguinal lymph nodes will also be undertaken.

An ECG will be done to exclude cardiac arrhythmia or palpitations [e.g., supraventricular tachycardia, atrial fibrillation, frequent ectopy, or sinus bradycardia (i.e., <50 beats per minute on exam)]

7.2.2 Sexual History and Genital Infection Screen

A sexual history will be taken for the preceding 6 month period, and participants will be asked whether they have ever been tested for sexually transmitted infections in the past and if so, whether any were found.

The following will be collected in all participants

- serology for syphilis
- serology for markers of hepatitis B surface antigen and hepatitis C antibody
- urine for Chlamydia and gonorrhoea at screening.

Other gonorrhoea and chlamydia tests will be collected if indicated on account of risk and symptoms, at the discretion of the PI.

7.2.3 Routine Laboratory Parameters

Peripheral blood will be collected by clinical staff experienced in phlebotomy into the appropriate containers and transported to the local laboratory.

Mid-stream urine will be collected into a sterile container and either tested on site (urine dipstick and pregnancy tests) or transported to the local laboratory. All laboratory assessments will be performed by Imperial College Healthcare NHS Trust.

The following parameters will be collected in all participants:

- Hb, total WBC, neutrophils, lymphocytes and platelets
- Creatinine, total and conjugated bilirubin (conjugated only if indicated) , alkaline phosphatase, AST, ALT and glucose
- Urinalysis using a dipstick for protein, ketones, blood, leukocyte esterase, and nitrites

- and for women of child-bearing potential only
- Urine test to exclude pregnancy

A urine specimen will be sent to the laboratory if the level of protein, blood, leukocyte esterase or nitrites is considered clinically relevant.

7.3 Immunogenicity Assessments

Samples will be collected at the timepoints specified in **Table 5** and transferred to the Immunology Core Laboratory for analysis.

7.3.1 Mucosal Specimens

Rectal secretions will be collected from male and female volunteers using an ophthalmic sponge. The sponge will be pre-moistened with sterile normal saline and inserted into the rectum using a proctoscope. Sponges will be held against the rectal wall for up to 2 min. Should a participant not wish to have proctoscopy the sponge may be inserted by the nurse or doctor 3 cm into the anal canal for 2 minutes.

Vaginal secretions will be collected from female volunteers using the INSTEAD Softcup, a commercially available, self-inserted menstrual cup made of polyethylene. Mucosal secretion collection will occur at the time points indicated in Table 5, except at visits when female volunteers are menstruating in which case vaginal secretions will not be collected.

